6.1 Treatment – Computerized Training

6.1.1 Identity of Investigational Treatment

The Alcohol AAT is a joystick-task that measures automatic approach tendency toward alcohol. The proposed Alcohol AAT was developed based on the previous work of Wiers et. al., (2009)^{10,12} and Rink et al., (2007)⁵⁰.

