6.2.2.1 Adverse Events Definition and Reporting

Adverse Events

During the study, site personnel will note any change in the condition(s) and the occurrence and nature of any adverse events. Important clinical information that comes to light during study participation will be communicated by research coordinators to the study physician in real time.

The study physician (either the PI, [name]) will review each participant's safety at each study visit.

- Lab results will be reviewed on the same day that the results are received.
- Adverse effects reported by participants will be reviewed on the same day as they are reported by the study participant.
- Adverse effect assessment will be done by the research coordinators and discussed with the study physician on a daily basis, immediately after these adverse effects are reported by the participant to the study coordinator.

As with our current, CHR-approved clinical trials, the study physician, if not immediately present at the time of adverse effect data collection, will be contacted in real time by the study coordinator by phone, pager, or text message, so that adverse effects can be discussed with the study physician. The study physician, based on examination of the participant and/or review of the participant's data, will make a clinical judgment at each visit regarding whether it is safe to proceed with study medications.

The PI will report to the IRB, DSMB and study sponsor his assessment of the potential relatedness of each AE to protocol procedure, studied disease state, study drug via the CRF. For each adverse event recorded on the Adverse Event CRF, the PI will make an assessment of seriousness, severity, and causality.

According to the ICH guideline for Good Clinical Practice, an adverse event is any untoward medical occurrence in a clinical investigation participant administered a pharmaceutical product, regardless of causal attribution. An adverse event can therefore be any of the following:

- Any unfavorable and unintended sign (including an abnormal laboratory finding), symptom, or disease temporally associated with the use of a medicinal product, whether or not considered related to the medicinal product.
- Any new disease or exacerbation of an existing disease (a worsening in the character, frequency, or severity of a known condition).
- Recurrence of an intermittent medical condition (e.g., headache) not present at baseline.

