- Any deterioration in a laboratory value or other clinical test (e.g., ECG, X-ray) that is associated with symptoms or leads to a change in study treatment or concomitant treatment or discontinuation from study drug. If a participant's dosage is reduced or treatment is discontinued as a result of an AE, the PI will report to the study sponsor via CRF the circumstances and data leading to any such dosage reduction or discontinuation of treatment.

Events leading to the clinical outcome of death from progressive disease will not be recorded as adverse events unless the PI believes that the event may have been caused by the study drug.

Serious adverse event (SAE) collection begins after the participant has signed informed consent and has received study drug. If a participant experiences an SAE after signing informed consent, but prior to receiving study drug, the event will NOT be collected unless the PI feels the event may have been caused by a protocol procedure.

The PI will alert the study sponsor of any SAE within 24 hours of the PI's awareness of the event. Alerts issued via telephone will be immediately followed with official notification on study-specific SAE forms.

An SAE is any adverse event from this study that results in one of the following outcomes:

- death (excluding death due to progression of study disease, unless related to study drug);
- initial or prolonged inpatient hospitalization;
- a life-threatening experience (that is, immediate risk of dying);
- persistent or significant disability/incapacity;
- congenital anomaly/birth defect;
- considered significant by the PI for any other reason.

Important medical events that may not result in death, be life-threatening, or require hospitalization may be considered serious adverse drug events when, based upon appropriate medical judgment, they may jeopardize the participant and may require medical or surgical intervention to prevent one of the outcomes listed in this definition.

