Serious adverse events (SAEs) occurring after a participant has taken the last dose of study drug will be collected for 7 days after the last dose of study drug, regardless of the PI's opinion of causation. Thereafter, SAEs will not be reported unless the PI feels the events were related to either study drug, or drug delivery system, or a protocol procedure. Any SAE occurring prior to enrollment that the PI believes may have been caused by a protocol procedure will be reported to the study sponsor within 24 hours of the PI's awareness of the event and recorded on the CRF.

Study-specific clinical outcomes of death from progressive disease will be reported as SAEs only if the PI deems them related to use of the study drug.

Immediate Reporting Requirements From

PI to Sponsor:

Certain events will be immediately reported to allow the Sponsor to take appropriate measures to address potential new risks in a clinical trial. The PI will report such events to the Sponsor immediately; under no circumstances will be reporting take place more than 24 hours after the PI learns of the event. The following is a list of events that the PI will report to the Sponsor within 24 hours after learning of the event, regardless of relationship to study providers:

Serious adverse events

Non-serious adverse events of special interest

Pregnancies

The PI will report new significant follow-up information for these events to the Sponsor immediately (i.e., no more than 24 hours after becoming aware of the information). New significant information includes the following:

- New signs or symptoms or a change in the diagnosis;
- Significant new diagnostic test results;
- Change in causality based on new information;
- Change in the event's outcome, including recovery;
- Additional narrative information on the clinical course of the event.

Emergency Medical Contracts

Medical Monitor Contact Information:

Any life-threatening (i.e., imminent risk of death) or fatal AE that is attributed by the PI to the investigational product will be telephoned to the Medical Monitor immediately, followed by submission of written case details on an CRF within 24 hours.

The following is the contact information that will be utilized by the PI:

MEDICAL MONITOR

[name], MPH

SFVAMC/UCSF

[name]

[name]

[contact] [name]

Email: [contact]

Follow-up of Participants after Adverse Events

PI Follow-Up:

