- Adverse Effects: Spontaneous: At Entry and at Human Lab Session 1 and 2; Phone visits 1 and 2; AABM Sessions 1-6; 1-wk FU. This form is designed to collect information about adverse health events. We will ask about emergent AEs, follow-up with AEs reported at previous study visits, and ask if there has been a hospital admission since the last study visit.
- Timeline Followback (TLFB): at study entry, then Human Lab Session 1 and Human Lab Session 2. TLFB will be used to calculate standard drinks consumed per week in the past 30 days prior to consent and at the two Human Lab Sessions, and the 1-week follow-up. The TLFB will be used to determine whether subjects meet minimum alcohol consumption criteria at entry. Other substance use will also be collected by TLFB.
- Barratt Impulsiveness Scale (version 11) (BIS-11) [98]: This provides a trait measure of impulsiveness and will be used to characterize the study cohort at study entry.

At AABM Training Sessions:

- Alcohol Use Disorders Identification Test (AUDIT): The AUDIT [97] is valid and reliable self-report measure of alcohol-related problem severity.
- Obsessive Compulsive Drinking Scale (OCDS): At AABM sessions 1 and 6. A questionnaire that measures cognitive aspects of alcohol craving.

- Alcohol Purchase Task (APT): At AABM sessions 1 and 6. A questionnaire uses hypothetical choices regarding alcohol purchases at varying prices to generate several indices of alcohol-related reinforcement.

At Follow-up visit:

- Motivational Enhancement Therapy: at the follow-up visit, research clinician will provide a motivational enhancement session to encourage the non-treatment seeking participants to consider treatment.

Measures of Alcohol Effects:

- Breath alcohol concentration (BrAlc) [99] *at each visit, and multiple times in ADP Sessions 1 and 2*. BrAlc will be measured at each session to detect recent alcohol use with the *Intoximeters Alco-Sensor IV* instrument.
- Blood Alcohol Levels: Human Lab Sessions 1 and 2 (Table 1): Blood samples will be drawn to measure plasma levels of blood alcohol (BAC) during the priming dose and during the alcohol self-administration paradigm. Blood samples will be stored at -4°C and will be analyzed at the San Francisco VA.

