7.4 Data Safety Monitoring Plan

Plan to monitor study progress and safety: The Data and Safety Monitoring Plan (DSMB)

The DSMP for this project consists of:

- a Data and Safety Monitoring Board (DSMB)
- a schedule of DSMB meetings to review study data and events

- a list of study data and event items to be reviewed by the DSMB
- procedures for communicating DSMB findings to the CHR, the study sponsor (Department of Defense) and other appropriate entities
- a plan for conducting and reporting interim analysis
- stopping rules
- rules for withdrawing study participants from the study interventions

These elements of the DSMP are described below:

The Data and Safety Monitoring Board (DSMB)

The Data and Safety Monitoring Board (DSMB) is a group of 3 physicians who are not study investigators and who are experts in the area of clinical research and substance use disorders. The current composition of the PI's DSMB is: [name]., a clinical investigator and Medical Director, PTSD Clinic, SFVAMC; [name]. [medical Monitor], an experienced human clinical investigator, Assistant Professor of Psychiatry at University of California, San Francisco and [name]., Ph.D., an experienced basic neuroscience investigator and attending psychiatrist, SFVAMC.

The DSMB will meet biannually to review data reports prepared by the PI regarding the progress of the study and will monitor patient enrollment, retention, outcomes, adverse events, and other issues related to patient safety. The DSMB will make recommendations to the PI as to whether the study should continue or be modified or terminated. The DSMB can consider patient safety or other circumstances as grounds for early termination. Any member of the DSMB can ask for a meeting of the group if he/she feels that it is necessary, based upon the data.

During the course of the study, reports will be prepared and distributed to the Data and Safety Monitoring Board on a biannual basis. In order for the Data and Safety Monitoring Board to discharge their duties for overseeing the study and the rights of the patients, they will receive analyses of the primary outcome measures and the important secondary measures on a quarterly basis. The DSMB will receive reports of serious adverse events (SAEs) within 72 hours of their occurrence.

DSMB Minutes will be prepared by the Study Coordinator within 5 working days after each biannual DSMB meeting.

Medical Monitor

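### Section 6.2.2.1 opens and closes causality-blind SAE collection on a study drug that this trial neither defines nor gives, and it conflicts with the plan's other safety rules

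*Combined protocol and SAP*

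**What the plan says.** Section 6.2.2.1 sets the start of SAE collection: "Serious adverse event (SAE) collection begins after the participant has signed informed consent and has received study drug". For an SAE after consent but "prior to receiving study drug, the event will NOT be collected unless the PI feels the event may have been caused", the cause in question is a protocol procedure. At the other end, SAEs after the last dose "will be collected for 7 days after the last dose of study drug, regardless of the PI's opinion of causation". Later SAEs are reported only if the PI thinks them related.

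No section identifies a study drug. Section 6.1.1, which is meant to identify the investigational treatment, says: "The Alcohol AAT is a joystick-task that measures automatic approach tendency toward alcohol". Section 6.1.3 gives active AABM training to everyone. Lacosamide appears once, in the consent-risk text of 3.3.2. Study medications are mentioned in 3.3.1, 6.2.2.1 and 6.3.5. None of these places gives a product with a dose, schedule or supply.

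Other safety provisions carry no such gate:
- Section 6.2.2.1, on AEs: "The PI will report to the IRB, DSMB and study sponsor his assessment of the potential relatedness of each AE". Each recorded AE is also rated for seriousness, severity and causality.
- Section 6.3.5: "Adverse Effects: Spontaneous: At Entry and at Human Lab Session 1 and 2; Phone visits 1 and 2", continuing through all AABM sessions and the one-week follow-up. At these contacts staff also "ask if there has been a hospital admission since the last study visit".
- Section 7.4: "The DSMB will receive reports of serious adverse events (SAEs) within 72 hours of their occurrence". The Medical Monitor reviews SAEs and states whether she agrees with the PI's report.
- Section 6.2.2.1 again: the sponsor is to be alerted within 24 hours to every SAE, and a later list repeats this whatever the relationship to the study.

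**The concern.** Safety is part of the first two Primary Aims in 4.2. The rule that decides which serious events are collected depends on an event, receipt of study drug, that does not occur in this trial as described. Two coordinators could follow the protocol faithfully and record different SAEs, one applying the collection clauses and the other applying the AE form and the reporting rules.

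What is at stake is mainly independent review. Under 7.4 the Medical Monitor gives a second opinion on each SAE, and an event that either she or the investigator finds possibly related goes forward to the IRB. If an unrelated verdict by the PI decides whether the SAE is collected at all, that second opinion may never be sought.

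**Working it through.** No figure in the plan bears on this point. Section 6.4.1 rules out inferential statistics and 6.4.2 gives sample size as not applicable. The check is to lay the SAE window over the visit order in 5.1.1 and 6.3.1 under each possible meaning of study drug. The two schedules differ in length (6 weeks in 5.1.1, 5 in 6.3.1) but agree on the order: consent and screening, ADP session 1, training, ADP session 2, follow-up. Section 5.1.1 puts follow-up 7 days after ADP session 2.

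1. **Literal reading: no drug is given.** The start condition is never met and the 7-day clause is never triggered. The pre-drug rule applies throughout, so from consent to follow-up only SAEs that the PI thinks a protocol procedure may have caused are collected.

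2. **Study drug means laboratory alcohol (assumption).** The window opens with the priming drink at ADP session 1. If ADP session 2 falls on day A, the window closes on day A + 7, and follow-up is also on day A + 7, so the two coincide. Only unrelated SAEs between consent and ADP session 1 are outside. This reading fits best: alcohol is the one substance the trial gives, 3.3.2 speaks of a priming dose, and the 7-day tail matches the follow-up visit. The text does not state it, however, and the vital-signs item in 6.3.5 treats study medications as something used alongside alcohol.

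3. **Study drug means AABM training (assumption).** The window opens after ADP session 1, so unrelated SAEs during screening and at that session are outside. Let T be the day of the last training session and d the days from then to ADP session 2, with d > 0 because ADP session 2 follows training. The window closes on T + 7. ADP session 2, on T + d, is inside only if d is 7 or less. Follow-up, on T + d + 7, is always after the window closes.

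4. **Study drug means the AAT, as 6.1.1 might suggest (assumption).** Section 5.1 has the AAT given before the drinking procedure in session 1, so the window is open by then. Its end depends on the last AAT, which the visit table in 6.3.5 does not show.

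Under the first three readings at least one stretch of time remains, consent to ADP session 1, in which 6.3.5 has staff asking about AEs and hospital admissions while 6.2.2.1 says that an unrelated SAE is not to be collected. Under the fourth, the same holds from consent until the AAT is first given.

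The conflict also lies inside 6.2.2.1. The collection clauses exclude unrelated SAEs outside the window, whereas the sponsor-reporting sentences cover all SAEs. Nothing says which prevails. The 72-hour rule in 7.4 governs reporting, so it implies collection rather than defining it. The direct collection conflict is with the AE rules in 6.2.2.1 and 6.3.5.

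**The case against.** The strongest reply is that little would be missed in practice. Four parts of it deserve an answer.

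*Other rules already catch every event.* Much of this stands. AEs are noted throughout and rated for seriousness, and hospital admissions are asked about from entry to follow-up. A reader might infer that unrelated SAEs would drop out of the safety summary. The documents do not support that: 6.4.3.3 summarises adverse effects descriptively and sets no SAE-window condition. What remains is that explicit text says not to collect certain SAEs, and no rule of precedence is given.

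*Events that matter are collected anyway.* This also stands. The PI need only think that a procedure may have caused the event, and both the alcohol sessions and the training are protocol procedures. The residual risk is misattribution by the PI, which is what the DSMB and Medical Monitor are there to check.

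*Stopping decisions are unaffected.* A reader might infer that the gate disables the stopping rules. It does not. The example in 6.3.6 and the pause in 7.5 both concern SAEs judged related. The narrower point is that the DSMB and the Medical Monitor can judge only events that reach them.

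*Excluding unrelated SAEs before treatment is a stated choice.* That is fair. The objection to it is only that 6.2.2.1, 6.3.5 and 7.4 do not apply it consistently.

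**Conclusion.** The defect is real and sits in operative text. Its extent depends on what study drug means. Read literally, the whole period from consent to follow-up is subject to PI attribution; on the best-fitting alcohol reading, only consent to ADP session 1 is. The alcohol reading is an assumption, because no section states it. Under any reading the collection clauses conflict with other current provisions, and a PI judgment could keep an SAE from independent review.

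Two stronger conclusions are not warranted. A reader might see a compromised primary endpoint because safety is in the Primary Aims, but 5.2.1 and 6.4.3.1 list only time and retention as primary outcomes and analyses, so no primary analysis changes. A reader might also want to express the gap as a change in an SAE rate, but the documents give no expected rate to support one. This is a safety-collection wording problem that should be corrected by amendment. It does not undermine the design.

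**What to change.** In 6.2.2.1, replace study drug, as both the start and the end of SAE collection, with the actual study interventions: laboratory alcohol and AABM training. State that SAEs are collected whatever the PI's view of causation, at least from the first intervention (ADP session 1) through the follow-up visit 7 days after ADP session 2.

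Reconcile the rule for the time between consent and ADP session 1 with the AE rules in 6.2.2.1 and 6.3.5 and with the DSMB and Medical Monitor provisions in 7.4. Collecting from consent is the simpler way to align them and adds no visit, because 6.3.5 already asks about AEs at entry. If the sponsor prefers to keep the pre-intervention exclusion, the other sections need to say so.

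Apply the same wording to the AE definition in 6.2.2.1, which is still tied to administration of a pharmaceutical product. Otherwise the new SAE trigger would rest on a definition with the same fault.

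The cost is an amendment to the text and a few more unrelated SAEs to record and report. No visit, assessment or analysis is added.

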4.3 Secondary Objectives

The Secondary Aim is to obtain a preliminary assessment of the effects of Alcohol Approach Bias Modification training on alcohol consumption and related behaviors in individuals with AUD.

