5.3.2 Eligibility Criteria

Inclusion Criteria:

1. Men, ages 21-50;
2. Able to read English and to complete study evaluations;
3. Heavy (also known as risky, high-risk, or hazardous) alcohol use, defined as 15-70 standard drinks per week on average over the past 30 days;
4. No more than 3 days/week of alcohol abstinence in the past 30 days, to maximize likelihood that participants will choose to drink during the laboratory sessions.
5. At least 1 heavy drinking day (\geq 5 drinks/day) per week on average during the 30 days prior to screening.

Exclusion Criteria:

[figure not shown]
1. Individuals who are seeking AUD treatment or have been in treatment within the past 6 months;
2. Current DSM-V non-alcohol substance use disorder other than tobacco and marijuana;
3. Positive urine drug test results at more than one baseline appointment for opioids, cocaine, benzodiazepines, or barbiturates;
4. Regular use of psychoactive drugs including antipsychotics, anxiolytics and antidepressants during the 30 days prior to entry, as well as anticonvulsants, beta blockers, central nervous system stimulants or depressants, or other drugs that cause excessive sedation;
5. Psychosis or any other serious mental illness as judged by MINI and study physician assessment;

6. Medical conditions that in the judgment of the study physician contraindicate the consumption of alcohol or would make study participation hazardous;
7. History of serious alcohol withdrawal (e.g. seizures, DTs, hospitalization) or a Clinical Institute Withdrawal Assessment Scale (CIWA-AD) score ≥ 8 ;
8. Participants who report disliking beer will be excluded because beer will be provided during the alcohol self-administration periods.

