[name]., Medical Director of the PTSD Clinic at San Francisco VA Medical Center will serve as the Medical Monitor. As Medical Monitor, [name] will review all unanticipated problems involving risk to subjects or others, serious adverse events and all subject deaths associated with the protocol and provide an unbiased written report of the event. At a minimum, the medical monitor will comment on the outcomes of the event of problem and in case of a serious adverse event or death, comment on the relationship to participation in the study. The Medical Monitor will also indicate whether she concurs with the details of the report provided by the principal investigator. Reports for events determined by either the investigator or medical monitor to be possibly or definitely related to participation and reports of events resulting in death will be promptly forwarded to the IRB and other governing authorities.

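### Section 6.2.2.1 exempts deaths from an undefined progressive disease from AE and SAE recording, so a death attributed to drinking or AUD could be left out of the safety record

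*Combined protocol and SAP*

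**What the plan says.** The exemption appears three times in section 6.2.2.1, each time with attribution to the study drug as its only exception.

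- AE recording: "Events leading to the clinical outcome of death from progressive disease will not be recorded as adverse events unless the PI believes" that the study drug may have been the cause.
- SAE list, first item: "death (excluding death due to progression of study disease, unless related to study drug".
- SAE reporting: "death from progressive disease will be reported as SAEs only if the PI deems them related to use of the study drug".

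Section 6.3.6 also lists evidence of progressive disease as a reason to discontinue a participant.

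The condition under study is described in two ways. The secondary aim in section 4.3 concerns the effects of "training on alcohol consumption and related behaviors in individuals with AUD". The inclusion criterion in section 5.3.2 is "Heavy (also known as risky, high-risk, or hazardous) alcohol use, defined as 15-70 standard drinks per week on average over the past 30 days", with no AUD diagnosis required. Section 4.2 makes the safety of administering alcohol in the laboratory the first primary aim.

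Section 7.4 has its own provision for deaths. The Medical Monitor reviews unanticipated problems, "serious adverse events and all subject deaths associated with the protocol and provide an unbiased written report of the event", and "reports of events resulting in death will be promptly forwarded to the IRB and other governing authorities".

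**The concern.** A disease-progression exemption presupposes a disease with a defined course and a drug whose effects can be told apart from that course. This study has neither. The condition is alcohol use, and alcohol is also what participants are given at both laboratory sessions. Section 3.3.2 acknowledges that acute alcohol can worsen liver disease, pancreatitis and other conditions, and treats heavier drinking during the study as a risk to guard against. A fatal worsening of an alcohol-related condition could therefore be seen either as the participant's own condition or as a harm of taking part. The rule lets the first view remove the event from the safety record, and the PI, who is also the study physician, makes that call.

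At stake is whether the AE and SAE record can support a statement about safety. A pilot with a safety aim should not have a rule under which a death on study need not be entered as an adverse event.

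**Working it through.** The plan gives no figure that bears on this point: section 6.4.1 rules out inferential statistics and section 6.4.2 marks sample size as not applicable. The check sets the provisions side by side.

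1. **Are the terms defined?** No. Progressive disease, study disease and study drug have no definition. The investigational treatment in section 6.1 is computerized training. The only drug that participants are described as taking is lacosamide, in the unknown-risks text of section 3.3.2, and it has no place in this design.

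2. **Does the exception bring back deaths due to study procedures?** Not clearly. Elsewhere in section 6.2.2.1, the rules for SAEs before study drug and for SAEs more than 7 days after the last dose name a protocol procedure as a ground for reporting. The three death exemptions do not. If alcohol is read as the study drug, a death that the PI links to the administered alcohol is restored. The documents do not say that it should be read that way. On either reading, a death attributed to the participant's own drinking or AUD stays exempt.

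3. **Do the other SAE criteria recover the event?** Not clearly. An SAE must first be an adverse event, and the first exemption acts at that level, on the events leading to the death. Hospitalization, threat to life and the PI's view of significance all apply only to something already counted as an AE. The same section counts exacerbation of an existing disease as an AE, so a non-fatal worsening is recorded while a fatal one may not be.

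4. **Does the rule on causation help?** No. SAEs within 7 days of the last dose are collected whatever the PI thinks of cause, but the exemption decides beforehand whether the death is an SAE at all.

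5. **Which channels depend on the event being an AE or SAE?**

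| Channel | Section | Trigger | Affected? |
|---|---|---|---|
| AE/SAE record on the CRF | 6.2.2.1 | AE or SAE as defined | Yes |
| Sponsor alert within 24 hours | 6.2.2.1 | SAE | Yes |
| DSMB report within 72 hours | 7.4 | SAE | Yes |
| Medical Monitor review | 7.4 | Unanticipated problem, SAE, or death associated with the protocol | Only in part |
| Study stopping | 6.3.6 | Safety judgment of the DSMB or PI | No |
| DSMB periodic review | 7.4 | Retention, outcomes, adverse events, other safety matters | Only in part |

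The pause in section 7.5 uses a different term, a serious adverse effect judged study-related by the PI and DSMB. A death that the PI attributes to drinking would not meet it on the PI's view in any case, so it is not counted here.

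**The case against.** The best defence is that this is leftover template text, like the references to study medications and a drug delivery system, and that section 7.4 already covers deaths. Much of that stands.

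- **A reader might infer that an exempted death would escape all oversight.** The documents do not support this. Section 7.4 lists deaths alongside SAEs as a separate trigger for the Medical Monitor, and the stopping provision in section 6.3.6 gives multiple SAEs only as an example. The death would also show as a loss in retention, a primary outcome under section 5.2.1.
- **A reader might infer that sections 6.2.2.1 and 7.4 are incompatible.** They are misaligned. One governs recording and reporting to the sponsor, the other the Monitor's review and forwarding to the IRB, and both can be followed at once.
- **A reader might infer that a fatal intoxication in the laboratory, or an injury, would be exempt.** Progression describes such acute events poorly, and section 5.3.2 excludes men with serious past withdrawal or conditions that contraindicate alcohol. The wording fits more readily a death put down to the course of the participant's drinking or AUD.
- **Naming the alcohol and procedures in place of the study drug would close part of the gap.** This is true, since the AE exception needs only a belief that causation is possible. Deaths that the PI considers unrelated would still be exempt.

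The backstop has its own limit. The Monitor's review covers deaths associated with the protocol, a phrase left undefined, and it does not change what section 6.2.2.1 requires to be recorded. That the text is probably inherited explains it but does not disarm it: it is the current rule.

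**Conclusion.** The point holds for the AE/SAE record and its expedited reporting, and no further. A death that the PI attributes to heavy drinking or AUD could, under the rule as written, be missing from the adverse event record, the 24-hour sponsor alert and the 72-hour DSMB report.

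This rests on two assumptions: that staff apply section 6.2.2.1 literally, and that the PI judges the death to be due to the participant's condition and not to a study drug. The documents give no mortality figure, so no probability can be attached. With 12 men enrolled, up to 15 started, and five to six weeks on study (sections 5.3.1, 5.1.1 and 6.3.1), such a death is unlikely. The point should still be corrected, because safety is a primary aim and the SAE list attaches an exclusion to no outcome other than death. It is not shown that the exemption was deliberate or that a death would be concealed.

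**What to change.** Amend section 6.2.2.1 in three places: delete the sentence that keeps events leading to such a death out of the AE record, the parenthesis after death in the SAE list, and the sentence that limits their reporting as SAEs. In their place, state that every death on study is recorded and reported as an SAE whatever the PI's attribution, with causality assessed afterwards. This aligns the section with the Medical Monitor's remit in section 7.4. Define on study by events that occur in this trial, since receipt of a study drug gives no usable starting point.

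Reconcile the progressive-disease withdrawal criterion in section 6.3.6 with the rest of the protocol, since the term has no stated meaning for this condition.

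The cost is a short amendment and, at most, a rare extra SAE report. No analysis, sample size or visit changes.
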